APPENDIX 4. Scoring rules for multi-item scales in SF-36 (Ware 2007)

Response scores to different items in the SF-36 have different ranges of pre-coded numeric values. For some items, higher pre-coded values represent a more favorable health state (e.g. ‘1’ corresponds to “Yes, Limited a Lot” for item 3a and ‘3’ corresponds to “No, Not Limited at All”). However, for other items, higher pre-coded values represent worse health (e.g. ‘1’ for item 1 corresponds to “Excellent” and ‘5’ corresponds to “Poor”). To account for these differences in valence, raw pre-coded numeric item scores will be converted to final scores for which higher values always represent better health. Conversion rules are set forth in Table 3 below.

Table 3 Conversion of SF-36 (v2) Raw Item Score to Final Item Scores

Scale	Pre-coded Item Value					
Item Number	1	2	3	4	5	6
Physical Functioning						
3a through 3j	1	2	3	N/A	N/A	N/A
Role Physical						
4a through 4d	1	2	3	4	5	N/A
Bodily Pain						
7	6	5.4	4.2	3.1	2.2	1
8, if item 7 is non-missing and pre-coded value = 1	6	4	3	2	1	N/A
8, if item 7 is non-missing and pre-coded value = 2	5	4	3	2	1	N/A
through 6						
8, if item 7 is missing	6	4.75	3.5	2.25	1	N/A
General Health						
1	5	4.4	3.4	2	1	N/A
11a and 11c	1	2	3	4	5	N/A
11b and 11d	5	4	3	2	1	N/A
Vitality						
9a and 9e	5	4	3	2	1	N/A
9g and 9i	1	2	3	4	5	N/A
Social Functioning						
6	5	4	3	2	1	N/A
10	1	2	3	4	5	N/A

Role Emotional

5a through 5c

	1	2	3	4	5	N/A
--	---	---	---	---	---	-----

Scale Pre-coded Item Value

Item Number	1	2	3	4	5	6
-------------	---	---	---	---	---	---

Mental Health

9b, 9c, and 9f

	1	2	3	4	5	N/A
--	---	---	---	---	---	-----

9d and 9h

	5	4	3	2	1	N/A
--	---	---	---	---	---	-----

Health Transition

2

	1	2	3	4	5	N/A
--	---	---	---	---	---	-----

If one or more items in a given scale are missing for a given subject, responses will be imputed using the average value for that subject for all non-missing items in the scale, provided that 50% or fewer of the items in the scale are missing. For example, if a subject does not answer one item in the 5-item MH scale, the subject's average score across the four non-missing items will be used to impute the value for the one missing item. If more than 50% of the items in a multi-item scale are missing, however, the entire scale will be set to missing. For single-item measures, the final score will be set to missing if the item raw score is missing.

After conversion of raw item score to final item score and imputation of missing data, a raw score will be computed for each scale. This raw score will be the sum of the final scores for all items in that scale. Raw scale scores will then be transformed into standardized scores, with a range from 0 to 100 (Note: raw and transformed scale scores are not calculated for the single-item Health Transition measure)

The lowest possible raw score and the possible raw score range of each multi-item scale are set forth in Table 4.

Table 4 Lowest/ Highest Possible Raw Scale Scores and Scale Raw Score Range

Lowest and Highest Possible Raw		
Scale	Scale Score	Scale Raw Score Range
Physical Functioning	10, 30	20
Role Physical	4, 20	16
Bodily Pain	2, 12	10
General Health	5, 25	20

Vitality	4, 20	16
Social Functioning	2, 10	8
Role Emotional	3, 15	12
Mental Health	5, 25	20

After transformation of raw scale scores to standardized scale score, the standardized scale score will be normalized as follows:

- PF Z-score (PF_Z) = (Transformed Score - 83.29094) / 23.75883
- RP Z-score (RP_Z) = (Transformed Score - 82.50964) / 25.52028
- BP Z-score (BP_Z) = (Transformed Score - 71.32527) / 23.66224
- GH Z-score (GH_Z) = (Transformed Score - 70.84570) / 20.97821
- VT Z-score (VT_Z) = (Transformed Score - 58.31411) / 20.01923
- SF Z-score (SF_Z) = (Transformed Score - 84.30250) / 22.91921
- RE Z-score (RE_Z) = (Transformed Score - 87.39733) / 21.43778
- MH Z-score (MH_Z) = (Transformed Score - 74.98685) / 17.75604

Scoring Rules for Overall Component

The two overall components will be computed as follows using the scale normalized scores:

- $PCS_Z = (PF_Z * 0.42402) + (RP_Z * 0.35119) + (BP_Z * 0.31754) + (GH_Z * 0.24954) + (VT_Z * 0.02877) + (SF_Z * (-0.00753)) + (RE_Z * (-0.19206)) + (MH_Z * (-0.22069))$
- $MCS_Z = (PF_Z * (-0.22999)) + (RP_Z * (-0.12329)) + (BP_Z * (-0.09731)) + (GH_Z * (-0.01571)) + (VT_Z * 0.23534) + (SF_Z * 0.26876) + (RE_Z * 0.43407) + (MH_Z * 0.48581)$

Transform composite scores PCS and MCS and 8 Z-score to :

Normalized scores = 50 + (Health Domain Z-score × 10)

- PF Normalized Score = 50 + (PF_Z * 10)
- RP Normalized Score = 50 + (RP_Z * 10)
- BP Normalized Score = 50 + (BP_Z * 10)
- GH Normalized Score = 50 + (GH_Z * 10)

Statistical Analysis Plan

GenSight Biologics

Version 10.0
Dated 10OCT2024

- VT Normalized Score = $50 + (VT_Z * 10)$
- SF Normalized Score = $50 + (SF_Z * 10)$
- RE Normalized Score = $50 + (RE_Z * 10)$
- MH Normalized Score = $50 + (MH_Z * 10)$
- PCS Normalized Score = $50 + (MCS_Z * 10)$
- MCS Normalized Score = $50 + (PCS_Z * 10)$

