If HVF is off then set to missing, if <0 set to 0.

The changes over time of each data point of HVF, with the following thresholds of gain or loss: ≥ 7 dB; 5-6.99 dB; 3-4.99 dB; ≤ 2.99 dB. Graphic mapping of HVFs per eye and per patient will be provided. Only reliable HVFs will be included in this analysis.

Contrast sensitivity measured with the Pelli-Robson Low Vision Contrast Sensitivity.

The last set of the 3rd secondary efficacy endpoint is the change from baseline at each time point in low vision contrast sensitivity as measured by the Pelli-Robson chart.

On-chart and off-chart contrast sensitivity

The Contrast Sensitivity score is calculated based on the last triplet of letters for which at least two of the three letters were read correctly (any result obtained past the triplet where the patient could not read at least 2 letters correctly is not to be recorded as the result). On-chart subjects are able to read at least two letters of the first triplet of the Pelli-Robson chart, and will thus have a CS value expressed in LogCS. Off-chart subjects are not able to read at least two letters of the first triplet of the Pelli-Robson chart, and will thus have no CS value. As no equivalent score exists for off-chart LogCS, 0 be assigned for eyes with off-chart LogCS.

Same analyses will be conducted on the LogCS instead of the change of LogCS for all eyes.

Quality of Life assessments

Visual Functioning Questionnaire-25

The VFQ-25 Questionnaire is a 25-item version of the 51-item National Eye Institute Visual Function Questionnaire. The VFQ-25 consists of a base set of 25 vision-targeted questions representing 11 vision-related constructs, plus an additional single-item general health rating question. All items are scored from 0 to 5 so that a higher number represents better functioning. To score the questionnaire, each item is converted to a 0-100 scale. Items within each subscale are averaged to create 12 subscale scores. The subscale scores (excluding the general health rating question) are then averaged to calculate the composite score (Mangione 2001), subscales with at least one item answered can be used to generate a sub-scale score. Hence, scores represent the average for all items in the sub-scale that the respondent answered. Items that are left blank (missing data) are not taken into account when calculating the scale score.

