By averaging the subscale scores rather than the individual items it will give equal weight to each subscale, whereas averaging the items would give more weight to scales with more items.

The secondary efficacy endpoint for VFQ-25 will be the change from baseline in the VFQ-25 composite score to each post-treatment follow-up visit.

Details of the conversion scale, sub-scales, calculations of the subscale scores and formula for averaging the subscale scores can be found in Appendix 4.

36-Item Short Form Health Survey, Version 2

The SF-36 Questionnaire is a generic, subject-reported outcome instrument used to assess QoL. The SF-36 is a 36-question instrument, which assesses 8 health concepts:

1. limitations in physical activities because of health problems;
2. limitations in social activities because of physical or emotional problems;
3. limitations in usual role activities because of physical health problems;
4. bodily pain;
5. general mental health (psychological distress and well-being);
6. limitations in usual role activities because of emotional problems;
7. vitality (energy and fatigue);
8. general health perceptions.

The scale score of each domain is calculated based on the summed score across items included in the domain and is rescaled to 0 to 100 with higher scores indicating better health states. The rescaled score of each domain is then normalized for the US population. Finally, the Physical Component Score (PCS) and Mental Component Score (MCS) will be computed using the normalized domain scores (Ware 2007).

Items that are left blank (missing data) are not taken into account when calculating the scale scores. Hence, scale scores represent the average for all items in the scale that the respondent answered.

The secondary efficacy endpoints for the SF-36 will be the change from baseline in each of the SF-36 domains as well as in the two composite scores to each post-treatment follow-up visit.

Details of the conversion rules, transformation scales, scale raw score range and scoring rules for overall component can be found in Appendix 5.

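### SAP Appendix 4 crosses the SF-36 physical and mental component scores in its last two lines; separately, the HVF floor at 0 does not say which parameters it covers

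*SAP*

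**What the plan says.** SAP section 13.2.1 fixes the meaning of the labels: "the Physical Component Score (PCS) and Mental Component Score (MCS) will be computed using the normalized domain scores". It makes change from baseline in both composites, as well as in the eight domains, a secondary endpoint at each follow-up visit. SAP section 13.2.3 analyses each composite with its own MMRM. These analyses serve secondary endpoint 5 (protocol section 8.2) and objective 8 (protocol section 7.2).

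SAP Appendix 4 scores the composites in three steps.

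- The physical Z-score has its large positive weights on the physical domains: "PF_Z * 0.42402) + (RP_Z * 0.35119) + (BP_Z * 0.31754) + (GH_Z * 0.24954". The mental Z-score has them on the mental domains: "SF_Z * 0.26876) + (RE_Z * 0.43407) + (MH_Z * 0.48581", plus vitality at 0.23534.
- The general rule is "Normalized scores = 50 + (Health Domain Z-score × 10", introduced as applying to PCS, MCS and the eight domain Z-scores. Each domain line uses its own Z, for example "PF Normalized Score = 50 + (PF_Z * 10".
- The last two lines are "PCS Normalized Score = $50 + (MCS_Z * 10" and "MCS Normalized Score = $50 + (PCS_Z * 10".

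The SAP version table records that version 9.0 (26OCT2021) added this normalisation step to correct an SF-36 calculation error. The crossed lines stand in version 10.0, the final version before database lock.

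On visual fields, SAP section 13.2.1 lists mean deviation, foveal threshold sensitivity and pattern standard deviation, and then states: "If HVF is off then set to missing, if <0 set to 0". The analysis of gain and loss at each data point of the field follows.

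**The concern.** Eight of the ten normalisation lines use the Z-score of the variable they name, and the two composite lines do not. A programmer working from these lines would report physical health under the mental label and the reverse, at every visit to Year 5. A reader would then credit or blame the wrong component of quality of life. Because the two sets of weights have opposite signs on several domains, a decline in one component can also show as a gain.

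The HVF sentence raises a different kind of problem. It names no parameter. If it were applied to mean deviation, and if mean deviation is negative in eyes with field loss, the floor would remove real change in that index.

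**Working it through.** **Is the swap real, or does it cancel?** If the Z-score labels had also been exchanged, the crossed last lines would undo it. They were not. The weights in Appendix 4 are:

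| | PF | RP | BP | GH | VT | SF | RE | MH |
|---|---|---|---|---|---|---|---|---|
| PCS_Z | 0.42402 | 0.35119 | 0.31754 | 0.24954 | 0.02877 | −0.00753 | −0.19206 | −0.22069 |
| MCS_Z | −0.22999 | −0.12329 | −0.09731 | −0.01571 | 0.23534 | 0.26876 | 0.43407 | 0.48581 |

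PCS_Z is a physical score and MCS_Z a mental score, as labelled, so the crossing stands.

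**Size.** The general rule gives PCS = 50 + 10 × PCS_Z. The printed line gives 50 + 10 × MCS_Z. The error in PCS is therefore 10 × (MCS_Z − PCS_Z), and the error in MCS is the same amount with the opposite sign.

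Physical domains (PF, RP, BP, GH) at −1 SD, the rest at 0:
- PCS_Z = −(0.42402 + 0.35119 + 0.31754 + 0.24954) = −1.34229, which gives 36.58
- MCS_Z = 0.22999 + 0.12329 + 0.09731 + 0.01571 = 0.46630, which gives 54.66

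All eight domains at −1 SD:
- PCS_Z = −0.95078, which gives 40.49
- MCS_Z = −0.95768, which gives 40.42
- Error in PCS = 10 × (−0.95768 + 0.95078) = −0.07 points

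| Profile (other domains at reference) | PCS by own Z | MCS by own Z | PCS as printed | MCS as printed |
|---|---|---|---|---|
| PF, RP, BP, GH at −1 SD | 36.58 | 54.66 | 54.66 | 36.58 |
| VT, SF, RE, MH at −1 SD | 53.92 | 35.76 | 35.76 | 53.92 |
| PF alone at −1 SD | 45.76 | 52.30 | 52.30 | 45.76 |
| MH alone at −1 SD | 52.21 | 45.14 | 45.14 | 52.21 |
| All eight at −1 SD | 40.49 | 40.42 | 40.42 | 40.49 |

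In the third row, a fall in physical functioning alone shows as a rise in PCS of 2.30 points instead of a fall of 4.24. Baseline values are crossed in the same way as follow-up values, so the two MMRM analyses are exchanged exactly: estimates, intervals and p-values.

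**HVF rule.** The documents give no mean deviation values, so the values here are assumed. With a floor at 0 applied to mean deviation before the change is taken:

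| Baseline to follow-up (dB, assumed) | Change with sign kept | Change after floor |
|---|---|---|
| −20 to −15 | +5 | 0 |
| −10 to −20 | −10 | 0 |
| −5 to +1 | +6 | +1 |

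Any eye negative at both visits shows a change of 0. Pattern standard deviation, being a standard deviation, should not fall below 0. For foveal and point-wise sensitivity, a floor at 0 may be what was intended.

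**The case against.** On the SF-36, the strongest reply is that Appendix 4 is formula text rather than program code, and that both the version log and the general rule state the normalisation correctly. A programmer may have followed the rule and not the last two lines. Both numbers are also computed correctly and can be recovered by relabelling, and the 18-point example is a profile chosen to separate the components. All of this stands. It limits what can be said about reported results and about the usual size of the error, but it does not make the two lines right.

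On the HVF rule, the sentence sits between the list of summary parameters and the point-wise analysis. References to off and sub-zero readings fit threshold values at least as well as a summary index. This also stands: the text leaves the scope open and does not direct the floor at mean deviation.

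On importance, SAP section 6.3 spends all the type I error on the primary endpoint and makes no multiplicity adjustment elsewhere. Neither point touches the trial's main conclusion.

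**Conclusion.** The SF-36 component formulas are wrong as written and need correction. That rests on the SAP's text alone. If the SAP is followed, PCS and MCS results are exchanged. The difference ranges from about 0.07 points when all domains shift together to about 18 points (54.66 − 36.58 = 18.08) when only the physical domains shift by 1 SD. Two of the ten SF-36 scores are affected. The eight domain scores, the VFQ-25, the primary endpoint, the sample size and the alpha are not.

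The HVF point is secondary and conditional. It matters only if the program applies the floor to mean deviation, and only on the assumption, not given in the documents, that mean deviation is negative in eyes with field loss.

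A reader might infer three stronger things that the documents do not support:

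- That SF-36 results already produced are wrong. No program or output is shown.
- That the direction of every composite effect is reversed. This depends on the profile.
- That the HVF endpoint can show neither benefit nor harm. At most one of three listed summary parameters is at risk, beside a separate point-wise analysis, and only eyes negative at both visits would be fixed at 0.

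**What to change.** In SAP Appendix 4, write PCS = 50 + (PCS_Z × 10) and MCS = 50 + (MCS_Z × 10). Check the scoring program against these lines, and re-run any PCS or MCS output that followed the crossed ones. The step entered in version 9.0, so outputs from that version onward are the ones to check.

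In SAP section 13.2.1, limit the floor at 0 to foveal threshold and point-wise sensitivities, and state that mean deviation is analysed with its sign. Check the HVF program and re-run mean deviation output only if the floor was applied to it.

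The cost is about three lines of text and two program checks. Version 10.0 is the final version before database lock, so the change needs a dated correction. Analyses are also planned at 1.5, 2, 3 and 4 years before the final one, so any earlier output found affected would have to be reconciled with the final tables.
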